15.2 Power Analysis

Based on our previous experience, we estimate the inter-subject coefficient of variation (CV) for the biomarkers listed in Table 1 to be between 30% and 40%. Biomarkers will be analyzed in the logarithmic scale; as a result, the standard deviation (SD) of the log of the level of these biomarkers is approximately equal to the CV in their original scale. For purposes of our power calculations, we will set the SD for each biomarker at 0.4 and assume a correlation of 0.5 between baseline and 6-week biomarker levels. The major hypotheses will be tested including only smokers who completely switch from smoking to SREC use. If a conservative estimate of only 50% of the 30 enrolled subjects achieving complete switching to SREC is applied, then 15 subjects would have greater than 90% power to detect a 45% decrease in the biomarker level in 6 weeks with a paired t-test. However, we incorporated measures to maximize the complete switching (as described in the Study procedures section) and will aim to have at least 20 subjects achieving this goal. The significance level was set at 0.001 due to multiple biomarkers being tested.

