
**Figure 1.** Urinary biomarkers to be analyzed in this study

In our preliminary published study on carcinogen and toxicant biomarkers in urine of 28 e-cigarette users who quit smoking 2-36 months before study entry (median 9 months), levels of NNAL, 1-HOP, 2-HPMA, 3-HPMA, and HMPMA were significantly lower in the urine of e-cigarettes users than in smokers.⁵³ In studies by Ruiz et al.⁵⁴ and Goniewicz et al.⁵⁵, in which cigarette smokers switched to e-cigarette use for 5 days and 2 weeks, respectively, significant reductions in the levels of these biomarkers were also observed. The findings of these three studies are summarized in Table 1. While all three studies show general decrease in toxicant and carcinogen exposures in e-cigarette users as compared to smokers, the inconsistencies in study designs (e.g., recruitment of current e-cigarette users vs. switching from smoking to e-cigarettes for various periods of time), the differences in e-cigarette brands and duration of use, and reported biomarker units make it difficult to clearly define these exposures in e-cigarette users and generalize the results to other e-cigarette products.

Formaldehyde-derived DNA adducts

As with most chemical carcinogens, DNA damage is critical in formaldehyde carcinogenesis because DNA adducts, if unrepaired, can cause mutations in critical genes such as *K-RAS* and *TP53*, leading to loss of normal cellular growth control mechanisms and cancer. Our group was the first to demonstrate the presence of a specific formaldehyde-DNA adduct, *N*⁶-hydroxymethyldeoxyadenosine (*N*⁶-HOCH₂-dAdo), in DNA from smokers' leukocytes. Measurement of this adduct in humans showed that its levels are related to smoking, with remarkable differences in *N*⁶-HOCH₂-dAdo being observed between smokers and nonsmokers.^{56,57} These adducts can be measured in DNA extracted from either blood or oral cells.⁵⁸

Table 1. Reported reductions in tobacco-related urinary biomarkers in e-cigarette users.

| Study | Our preliminary study ⁵³ 28 e-cigarette users who quit smoking 2-36 months before study entry; a variety of e-cigarette brands used. | | Ruiz et al. ⁵⁴ 15 smokers who completely switched to researchable Blu e-cigarettes with tobacco-flavored e-liquid containing 24 mg/mL nicotine. | | Goniewicz et al. ⁵⁵ 20 smokers who switched to M201 Mild e-cigarettes with tobacco-flavored cartridges containing 11 mg nicotine (only 9 complete switchers). | |

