In our preliminary study, we have found that levels of 8-*iso*-PGF_{2α} and PGEM are similar in the urine of e-cigarette users and cigarette smokers (same subjects as in Table 1). The median levels of 8-*iso*-PGF_{2α} were 0.80 pmol/mL urine (range 0.13-2.17, N=28) in e-cigarette users, the same as 0.80 pmol/mL (range 0.18-2.74, N=83) in cigarette smokers from a recently completed study. For PGEM, the median values (in pmol/mL) were 32.1 (5.0-184, N=28) in e-cigarette users vs. 31.4 (range 3.0-149, N=86) in cigarette smokers. This is in contrast with the expected decrease to normal levels after 2 weeks of smoking cessation.^{71;76-78} Our subjects used various e-cigarette brands and e-liquid types, and it is not clear whether the elevated levels of inflammatory and oxidative markers were due to exposures to high levels of formaldehyde from their e-cigarettes. Measurement of 8-*iso*-PGF_{2α} and PGE-M in the proposed study, in which subjects will use SREC e-cigarettes containing low levels of formaldehyde (0.1 µg per puff) and operating at a relatively low voltage (3.30 V), will eliminate this potential contributing factor and allow to examine

the potential capacity of the low-formaldehyde e-cigarette aerosol to sustain the high levels of systemic inflammatory state in former smokers.

Oxidative DNA damage is likely involved in tumor promotion and other harmful effects of smoking^{79,80}. Measurement of DNA adducts can offer a direct assessment of such damage. Direct oxidation of guanine produces 8-oxo-7,8-dihydro-2'-deoxyguanosine (8-oxo-dG), which is widely used as a biomarker of oxidative stress.⁸¹ We recently developed a highly sensitive LC-MS/MS method for the analysis of 8-oxo-dG in very small amounts of DNA,⁸² and will use this method to assess oxidative DNA damage in our study subjects. Circulating cytokines and chemokines, such as CRP, TGF α , IL6, IL8, and others, are well-established biomarkers associated with lung cancer and cardiovascular disease risk.⁸³ These systemic inflammation markers will be also assessed to provide a comprehensive oxidative and inflammatory profile in our study subjects.

Endogenous formation of NNN

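### Section 15.2 supports a log-SD of 0.4 only for the Table 1 biomarkers but states power as if for every biomarker, and the abstinent-completer target is 30 in two places and 20 in two others

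*Combined protocol and SAP*

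**What the plan says.** **Power.** Section 15.2 estimates the inter-subject "coefficient of variation (CV) for the biomarkers listed in Table 1 to be between 30% and 40" percent, and equates this with the SD on the log scale. It continues: "we will set the SD for each biomarker at 0.4 and assume a correlation of 0.5 between baseline and 6-week biomarker levels". The result is that "15 subjects would have greater than 90% power to detect a 45% decrease in the biomarker level in 6 weeks with a paired t-test", at a significance level of 0.001.

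**Which biomarkers.** The source of the CV is "Table 1. Reported reductions in tobacco-related urinary biomarkers in e-cigarette users" (Section 2.0), which lists NNAL, 1-HOP, 2-HPMA, 3-HPMA and HMPMA. Table 2, the list to be analysed, also has TNE, total NNN, PheT and CEMA under Aim 1, and DNA adducts, cytokines, 8-iso-PGF2α, PGE-M and the salivary markers under Aims 2 and 3. 1-HOP is in Table 1 but not in Table 2.

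**Printed spread.** For PGEM, the Background says "the median values (in pmol/mL) were 32.1 (5.0-184, N=28) in e-cigarette users vs. 31.4 (range 3.0-149, N=86) in cigarette smokers". For 8-iso-PGF2α, the medians "were 0.80 pmol/mL urine (range 0.13-2.17, N=28) in e-cigarette users, the same as 0.80 pmol/mL (range 0.18-2.74, N=83) in cigarette smokers".

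**Endpoint status.** Section 15.1 and the sentence above Table 2 make the inflammatory markers and DNA adducts primary. Section 3.2 and Secondary Aim 1 make them secondary. The Aim 3 markers are primary by the sentence above Table 2 and secondary by Section 3.2 and Secondary Aim 2.

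**Target.** The Study Summary gives 30 abstinent completers. Section 5.3 gives 30 completers with total abstinence for six weeks. Section 10.0 gives at least 30 completers, of whom 20 are abstinent. Section 15.2 allows for "only 50% of the 30 enrolled subjects achieving complete switching to SREC" and then "will aim to have at least 20 subjects achieving this goal".

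**The concern.** The SD drives the power figure, and Section 15.2 moves from a CV given for five urinary exposure markers to an SD for 'each biomarker' without further support. PGEM is outside Table 1, and its printed values span 37-fold and 50-fold, far more than a log-SD of 0.4 would normally produce in samples of those sizes.

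Secondary Aim 1 expects biomarkers of effect to fall from baseline, and the Background asks whether low-formaldehyde aerosol can keep inflammation high. A reader who takes the power of over 90% to cover PGEM would have more confidence in a null PGEM result than the protocol's own figures support.

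The two completer targets leave it unclear when recruitment has met its goal. They also leave unclear whether the 30 are enrolled, have completed, or have completed and stayed abstinent.

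**Working it through.** **1. Reproducing the plan's figure.** Inputs from Section 15.2: 45% decrease, log-SD 0.4, correlation r = 0.5, n = 15, alpha 0.001. The plan does not say one- or two-sided; two-sided is assumed here.

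- Effect on the log scale: -ln(0.55) = 0.598.
- SD of the paired change: SD × sqrt(2(1 - r)) = 0.4 × sqrt(1) = 0.4.
- Paired t-test power (noncentral t, n - 1 df): 91.2% at n=15, 99.2% at n=20, over 99.9% at n=30. One-sided, n=15 gives 95.3%.

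The stated figure is confirmed. The largest SD that keeps 90% power is 0.407 at n=15, 0.500 at n=20 and 0.648 at n=30.

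**2. Does PGEM fit 0.4?** For a log-normal sample, SD ≈ ln(max/min)/d2, where d2 is the expected range of N standard normal values (by simulation, 200,000 samples: 4.03 for N=28 and 4.91 for N=86).

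| PGEM sample | Fold range | ln(max/min) | Implied log-SD (95% limits) | Typical fold range at SD 0.4 | 97.5th percentile at SD 0.4 |
|---|---|---|---|---|---|
| E-cigarette users, N=28 | 184/5.0 = 36.8 | 3.605 | 0.90 (0.65-1.29) | 5.0 | about 9 |
| Smokers, N=86 | 149/3.0 = 49.7 | 3.905 | 0.80 (0.63-1.02) | 7.1 | about 12 |

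No simulated sample at SD 0.4 was as wide as either printed range. Median to maximum alone gives 0.87 and 0.64, so a low minimum does not explain the result.

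**3. PGEM power for a 45% decrease, r = 0.5, two-sided alpha 0.001.** The lower figure in each cell uses SD 0.895 and the higher 0.796; in the last two rows, 0.653 and 0.625. Averaging weeks 4 and 6, with all pairwise correlations taken as 0.5, multiplies the SD of change by sqrt((1 + r)/2 + 1 - 2r) = sqrt(0.75) = 0.866.

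| | n=15 | n=20 | n=30 |
|---|---|---|---|
| One visit, central SDs | 12-18% | 24-34% | 51-67% |
| Weeks 4 and 6 averaged, central SDs | 20-29% | 37-52% | 71-84% |
| One visit, lower-limit SDs | 34-39% | 59-65% | about 90-93% |
| Both visits averaged, lower-limit SDs | 51-57% | 78-82% | 97-99% |

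**4. Dependence on the correlation.** The documents give no PGEM correlation. At n=20, one visit, central SDs: 13-20% at r=0.3, 24-34% at r=0.5, 51-67% at r=0.7, 78-89% at r=0.8.

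**5. Urine dilution.** The printed values are per mL, and dilution adds spread. To bring PGEM down to 0.4, the share of log variance to remove is 1 - 0.16/SD²: about 75-80% at the central SDs and 59-62% at the lower limits. Section 15 names no dilution correction.

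**6. 8-iso-PGF2α.** The full range gives log-SD 0.70 (N=28) and 0.56 (N=83). The upper half alone gives about 0.50, where 0.4 is not ruled out (chance 0.17 and 0.09). Power at n=20 is 50-79% on the full-range SDs and 89-91% on the upper-half SDs.

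**7. Target.** At SD 0.4, 20 and 30 switchers both give at least 99% power. For PGEM, the choice moves one-visit power from 24-34% to 51-67%. Section 15.2 halves 30 enrolled subjects to reach 15, whereas in Section 5.3 the 30 are already abstinent, so halving them makes no sense there.

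**The case against.** **The wording may be narrower.** Section 15.2 runs from the Table 1 biomarkers to 'these biomarkers' to 'each biomarker', so the last phrase may mean the Table 1 set. PGEM then contradicts nothing. This stands as a fair reading, but it moves the gap: TNE, total NNN, PheT and CEMA (four of eight Aim 1 markers) have no stated power basis, and neither do the inflammatory markers and DNA adducts that Section 15.1 calls primary.

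**The trial is exploratory.** Section 15.1 says so, and nothing obliges a plan to power every secondary marker. That also stands. The request is to say which markers the power statement covers.

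**The size of the PGEM loss is soft.** It rests on extreme values, log-normality, per-mL concentrations and an assumed correlation, and one sample used various devices. The study collects first-morning urine; the Background does not say what kind of sample the earlier values came from. The planned model uses both visits. All of this stands, and it is why the result is given as a range.

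**A null result may not be misread.** A reader might infer that the plan will take a non-significant PGEM result as proof of no change. The documents do not say that; Section 15.1 already plans geometric means and reductions with confidence intervals.

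**Conclusion.** The concern holds as a limit on what Section 15.2 supports. The figure of more than 90% is correct at its inputs, and nothing here undermines it for total NNAL, 2-HPMA, 3-HPMA and HMPMA. On the wide reading of 'each biomarker', the printed PGEM ranges do not fit a log-SD of 0.4: even the lower limits are about 0.63-0.65. On the narrow reading, much of Table 2 has no power basis. The text needs correcting either way.

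That PGEM's spread exceeds 0.4 is well supported, given log-normality. The resulting power is not well determined, because the correlation and the effect of dilution correction are unknown. A reader might conclude that the trial is underpowered for PGEM by a known amount, or that 8-iso-PGF2α falls short too; the documents establish neither.

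The 30-versus-20 conflict is plain in the current text. A reader might infer that it weakens the stated power, but at SD 0.4 it does not. What it leaves undefined is the recruitment goal and the meaning of the 30.

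**What to change.** 1. **Section 15.2.** Limit the claim of more than 90% power to named biomarkers with a supported log-SD of about 0.4 or less. As the text stands, these are the markers in both tables: total NNAL, 2-HPMA, 3-HPMA and HMPMA. For the others, including TNE, total NNN, PheT, CEMA, PGEM and 8-iso-PGF2α, take the log-SD from the group's existing data where available. Then state power or the detectable decrease at the target n over a range of correlations, or say that no power is claimed. The range-based SDs above only show scale and should not be copied in.
2. **Target.** Use one abstinent-completer number, and one label for the 30 (enrolled, completers or abstinent completers), in the Study Summary and Sections 5.3, 10.0 and 15.2.
3. **Endpoint status.** Make the primary or secondary status of the inflammatory markers, the DNA adducts and the Aim 3 markers agree across the Aims, Sections 3.1 and 3.2, the sentence above Table 2, and Section 15.1.

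The cost is text edits and a short calculation on data the group already holds, with no added enrolment. The downside is a less favourable stated power for some markers.

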15.3 Data Integrity

A variety of measures will be taken to ensure data accuracy and completeness. The regular research team meetings will include discussions of proper methods for data

collection, transmission, and storage, limiting data collection to those in protocol required to answer a research question, de-identifying data, and encryption methods.

A comprehensive data dictionary will be created to specify definitions and value codes for all variables that will be entered into REDCap and other study databases. Electronic forms for the collection of subjective measures via REDCap will include programming features to ensure valid data (i.e., input masks, validation criteria, skipout logic) and will be stored on the University of Minnesota, HIPAA compliant, computing system. Double entry will be used for all other de-identified data entered into REDCap. Biological specimens will be labeled with barcode labels that incorporate the participant ID. The secured biospecimen website will identify the location of each sample at the clinic (prior to submission to the laboratory) and in the [name] laboratory.

Oversight of the product distribution will be conducted by the Project Manager in collaboration with the co-Principal Investigators. A Product Tracking database will be created. This database will be used to track product purchases, product inventory, and assignment of study product to participants.

Quality control procedures will be conducted for all data collected, including analysis of missing data, and logic checks for out of range and other anomalous values. Queries will be made regarding such data issues, with documentation of any changes made in the data.

16.0 Confidentiality

All investigators and staff associated with this project have been trained, and new hires will be trained, on human research ethics and Good Clinical Practice in accordance with the requirements of the University of Minnesota.

Only the Study Coordinator and Principal Investigators will have access to individually identifiable private information about subjects. Coded ID's will be used throughout the study by all the researchers involved. Because this study uses a research e-cigarette and we are required to submit an Investigational Tobacco Product application through the Food and Drug Administration, the records may potentially be monitored by this governmental agency. This information will be provided to the IRB and will be included in the human consent form.

17.0 Provisions to Monitor the Data to Ensure the Safety of Participants

17.1 Data Integrity Monitoring

Oversight for quality control and adherence to protocol procedures will be conducted by the Project Manager in collaboration with the co-Principal Investigators. A start-up meeting with whole research team will take place prior to participant enrollment. During this meeting, there will be training on the study protocol, standard operating procedures, equipment and data collection platforms. The co-Principal Investigators will closely monitor the research staff on the procedures to be used in this study. Such monitoring will consist of frequent in-person discussion of study visits and other procedures to make sure that all protocol procedures are followed, and regular research team meetings to

provide updates on study progress and review the data collection process, the results from data monitoring and other issues of concern.

Standard operating procedures will be developed for consistent implementation of the protocol. Study Coordinator will be administering all measures during clinic visits and entering the information about each subject into a database. Each visit will have a checklist of all measures that need to be obtained and the order by which they will be administered. Project Manager will be directly supervising the Study Coordinator and periodically review protocol compliance and implementation, and adherence to good clinical practice procedures.

The Study Coordinator will go over the questionnaire instructions and will be available to the participant to answer any questions he/she may have. Questionnaires will be reviewed for completeness while the participant is present. Other questionnaires are completed on the computer, so that participants cannot accidentally skip a question. However, they may choose not to answer questions. Several biochemical measures (expired breath CO and urine pregnancy) will be analyzed immediately, while the participant is present. If necessary (e.g., if the sample volume is insufficient for analysis), the Study Coordinator can gather another sample immediately and re-analyze.

Once a participant has completed all study procedures and all open events have been closed, the PI will review the participant's binder and sign a form indicating study completion for that participant.

17.2 Data Safety Monitoring

CTSI is responsible for periodically monitoring this study. While participating in the trial, AEs and concomitant medications will be assessed at every study visit and vital signs will be obtained periodically. AEs will typically be identified during the administration of the Health Changes Questionnaire and Respiratory and Global Health Questionnaire, and in some cases during the administration of the CES-D. Other events may be identified from physiological study measures or by spontaneous reports during assessments.

Assessment of Questionnaire Items

- Health Changes Questionnaire: If the participant answers 'YES' to Questions 1, 2, or 3, the interviewer will assess for an 'Adverse Event.'
 - 1) *Have you had any negative changes in your health since your last visit?*
 - 2) *Have you had any changes in medication since your last visit?*
 - 3) *Since your last visit, have you received any form of medical care?*
- Respiratory Health Questionnaire: If the participant indicates 'YES' to Question 6 regarding having a cold or flu the interviewer will administer the 'Adverse Event Log.'
 - 6) *In the past week, have you experienced any health problems, such as cold, flu, or other respiratory illness that would affect these respiratory symptoms?*
- CES-D: If the participant scores 16 or higher and are not already being monitored for depression, an 'Adverse Event' will be recorded and the licensed medical

professional will provide information regarding follow-up. If there is already an open event, information will be added to the existing 'Adverse Event.'

Assessment of Physiological Data

- **CO level:** An 'Adverse Event' will be recorded if the average of two consecutive measurements in the same visit is:
 - CO is greater than 50 ppm if CO at Baseline is < 20 ppm
 - CO is greater than 60 ppm if CO at Baseline is 20 – 34 ppm.
 - CO is greater than 70 ppm if CO at Baseline is 35 – 49 ppm.
 - CO is greater than 80 ppm if CO at Baseline is 50 – 64 ppm.
 - CO is greater than 90 ppm if CO at Baseline is 65 – 80 ppm.
- **Blood Pressure:**
 - The 'Adverse Event Log' and 'Blood Pressure and Heart Rate Symptom Checklist' will be completed if an automatic and subsequent manual blood pressure measurement during the same visit is at or above 160 systolic or 100 diastolic.
 - The 'Adverse Event Log' and 'Blood Pressure and Heart Rate Symptom Checklist' will be completed if an automatic and subsequent manual blood pressure measurement during the same visit is below 90 systolic or 50 diastolic and the participant is experiencing symptoms listed on the 'Blood Pressure and Heart Rate Symptom Checklist.'
- **Heart Rate:**
 - The 'Adverse Event Log' and 'Blood Pressure and Heart Rate Symptom Checklist' will be completed if an automatic and subsequent manual heart rate measurement during the same visit is at or above 105 bpm.
 - The 'Adverse Event Log' and 'Blood Pressure and Heart Rate Symptom Checklist' will be completed if an automatic and subsequent manual heart rate measurement during the same visit is below 45 bpm and the participant is experiencing symptoms listed on the 'Blood Pressure and Heart Rate Symptom Checklist.'

Adverse Events Communicated by Participants

The occurrence of AEs will be sought by non-directive questioning of the participant at each visit during the study. AEs also may be detected when the participant volunteers them during or between visits or through physical examination, laboratory test, or other assessments.

Review and Reporting of Adverse Events and Serious Adverse Events

Co-Principal Investigators with oversight from [name]. (Medical Monitor) and [name] (Nurse Practitioner) will review all AEs and assess whether they are related to the study product.

PROTOCOL TITLE: Biomarkers in SREC Users

VERSION DATE: 03/13/2024

An AE is defined as the appearance or worsening of any undesirable sign, symptom, or medical condition occurring after starting the study procedures even if the event is not considered to be related to the study product. Medical conditions/diseases present before starting the study are only considered adverse events if they worsen after starting the study product. Abnormal laboratory values or test results constitute adverse events only if they induce clinical signs or symptoms, are considered clinically significant, or require therapy; there are no plans for active monitoring of laboratory tests as part of this project. Withdrawal symptoms are considered adverse event if the symptom had a significant impact on the participant's daily life, caused a major disruption of functioning, or took any medication for it.

To the extent possible, each adverse event will be evaluated to determine:

1. the severity grade (mild, moderate, severe)
2. its relationship to the study product used (suspected/not suspected)
3. its duration (start and end dates or if continuing at final exam)
4. outcome (resolved/improved/unchanged/worsened; study product temporarily interrupted or permanently discontinued due to this adverse event; concomitant medication taken; non-drug therapy administered)
5. whether it constitutes a SAE

Information about all SAEs will be collected and recorded on the project's Serious Adverse Event Report Form. A SAE is defined an undesirable sign, symptom or medical condition which:

1. is fatal or life-threatening;
2. requires or prolongs hospitalization;
3. results in persistent or significant disability/incapacity;
4. constitutes a congenital anomaly or a birth defect;
5. is medically significant, in that it may jeopardize the subject and may require medical or surgical intervention to prevent one of the outcomes listed above.

Events not considered to be SAEs are hospitalizations that are:

1. elective or pre-planned, for a pre-existing condition that is unrelated to the products under study and did not worsen;
2. for general care, and/or overnight observation;
3. treatment on an emergency, outpatient basis for an event not fulfilling any of the definitions of serious given above and not resulting in hospital admission.

Safety evaluation will be performed on all accrued participants for whom SREC was dispensed. The assessment of safety will be based on the frequency of AEs and severity grade of AEs. Other safety data (e.g. CO, vital signs) will be considered as appropriate.

SAEs occurring after the participant has signed the consent form and until 4 weeks after the participant has stopped use of study product that are unexpected and at least possibly related will be reported. SAEs occurring more than 4 weeks after study discontinuation need only be reported if a relationship to study product is suspected. All AEs will be summarized by presenting, for each treatment group, the number and percentage of participants who experienced any AE, the number reporting AEs in each body system and

the number of AEs by type. Any other information collected (e.g., severity or relatedness to study medication) will be listed as appropriate. A summary of clinically relevant toxic events, such as AEs leading to death or rated as SAEs, those with a suspected relationship to study product, or AEs requiring further medication or non-drug therapies will be provided. Reports will be reviewed regularly by the study investigators and the NIDA Scientific Officer.

Data Safety Monitoring Plan administration

The Co-Principle Investigators will be responsible for monitoring the safety of this trial, executing the DSM plan for this project and complying with the reporting requirements.

Investigators will meet at least monthly throughout this project to review any recruitment, data quality, and safety issues. Specifically, they will assess enrollment information, demographics and characteristics of the participants, the expected versus actual recruitment rates, quality assurance or regulatory issues that may have occurred during the past month, protocol violations, and review AEs to determine if there are any changes in participant risk. Investigators are available to meet outside of the scheduled meetings, if concerns regarding a particular participant or another problem should arise.

The DSM report will include treatment group information. This includes enrollment information, demographics and characteristics of the participants, the expected versus actual recruitment rates, quality assurance or regulatory issues that may have occurred during the year, a summary of AEs and SAEs, protocol violations, and any actions or changes to the protocol. Also included will be any and all actions by the IRB.

